## 9. TREATMENT OF SUBJECTS

### 9.1. Study Drug Dose and Administration

Study drugs include:

- ALKS 3831 10/10 or 20/10 (10 mg olanzapine/10 mg samidorphan or 20 mg olanzapine/10 mg samidorphan respectively) administered as a coated bilayer tablet
- Olanzapine 10 mg or 20 mg administered as a coated bilayer tablet
- Placebo matching 10 mg and 20 mg tablets.

During the inpatient period, subjects will be administered study drug orally, once daily preferably at bedtime. Following discharge on Day 15 or later, subjects will be given study drug to take home and instructed to take one tablet orally preferably at bedtime. If there are tolerability problems, dosing may be switched to another time based on the judgment of the investigator; frequent switching is discouraged.

### 9.2. Treatment Adherence

Subjects will undergo a study drug adherence review at the time points indicated in [Table 1](#). In addition to these scheduled adherence reviews, for subjects discharged on Day 15 or 22, study staff will check in with them or a caregiver (if applicable) between assessment visits to monitor treatment adherence.

### 9.3. Randomization/ Method of Assigning Subjects to Treatment

Subjects meeting eligibility criteria at baseline (Day 1) will be randomized in a 1:1:1 ratio to one of the following treatment groups:

- ALKS 3831
- Olanzapine
- Placebo

Randomization will be performed centrally through an Interactive Web Response System (IWRS). A unique randomization number will be assigned by the IWRS once eligibility has been determined. Once a randomization number has been assigned, that number must not be used again if, for example, a subject is withdrawn from the study. Codes will be prepared by an independent biostatistician who is not otherwise involved in this study.

### 9.4. Blinding

All Alkermes staff, clinical staff, subjects and caregivers will be blinded to treatment assignment until database lock.

The principal investigator is responsible for all trial-related medical decisions. If the investigator deems it necessary to break the study blind in the interest of a subject's medical safety, he or she must make every effort to contact the CRO/ sponsor medical monitor before the blind is broken.

If the site is unable to contact the medical monitor prior to breaking the blind, the medical monitor must be contacted within 24 hours following disclosure of study drug assignment. Any premature unblinding should be promptly documented.

Breaking the blind for a single subject will not affect the blind for the remaining subjects.

## **10. STUDY DRUG MATERIALS AND MANAGEMENT**

### **10.1. Study Drug**

ALKS 3831 drug product will be supplied as a coated bilayer tablet in two fixed-dose combinations:

- ALKS 3831 10/10 (10 mg olanzapine/10 mg samidorphan)
- ALKS 3831 20/10 (20 mg olanzapine/10 mg samidorphan)

Matching olanzapine-only drug will be supplied as a coated bilayer tablet in two dose strengths:

- OLZ 10 (10 mg olanzapine)
- OLZ 20 (20 mg olanzapine)

Matching placebo will be supplied in two dose strengths:

- Placebo to match 10/10 ALKS 3831 and 10 mg olanzapine comparator
- Placebo to match 20/10 ALKS 3831 and 20 mg olanzapine comparator

### **10.2. Packaging and Labeling**

All tablets will be packaged in HDPE bottles with desiccant. Bottle labels will meet all applicable local and regulatory requirements.

### **10.3. Storage**

Product should be stored at not more than 25°C.

Under the US Controlled Substances Act, samidorphan is considered a Schedule II substance because it is derived from opium alkaloids. Therefore, samidorphan and/or blinded study drug must be stored in accordance with restrictions related to Schedule II substances. The site will take adequate precautions, including storage of the investigational drug in a securely locked, substantially constructed cabinet, or other securely locked, substantially constructed enclosure, access to which is limited, to prevent theft or diversion of the substance.

### **10.4. Accountability**

The clinical site is required to maintain current drug dispensation and accountability logs throughout the study. All unused supplies will be checked against the drug movement records during the study and/or at the end of the study.

Refer to [Section 8.3.15](#) for additional study drug reconciliation procedures.

### **10.5. Handling and Disposal**

Following completion and verification of accountability logs, all unused and used packages must be destroyed. Packages may be destroyed on site according to Good Clinical Practice (GCP) and site practice. Alternatively, the sponsor may arrange for destruction with a third party vendor operating in accordance with GCP and/or Good Manufacturing Practice (GMP), as applicable.

## **11. ASSESSMENT OF EFFICACY**

### **11.1. Efficacy Measures**

- Positive and Negative Syndrome Scale (PANSS) ([Kay, Fiszbein et al. 1987](#))
- Modified Overt Aggression Scale (MOAS) ([Kay, Wolkenfeld et al. 1988](#))
- Clinical Global Impression of Severity (CGI-S) ([Guy 1976](#))
- Clinical Global Impression of Improvement (CGI-I) ([Guy 1976](#))

See [Section 8.3.9.2](#) for details regarding efficacy assessments.

## **12. ASSESSMENT OF PHARMACOKINETICS AND PHARMACODYNAMICS**

Concentrations of olanzapine, samidorphan, and metabolites of interest will be determined from plasma samples collected according to the schedule in [Table 1](#). Pharmacokinetic (PK) data from these samples may be included in a subsequent population PK analysis conducted outside of this study. By-subject listings of plasma concentrations will be provided.

### 13. ASSESSMENT OF SAFETY

Safety will be assessed on the basis of:

- Adverse events
- Abnormal Involuntary Movement Scale (AIMS)
- Barnes Akathisia Rating Scale (BARS)
- Simpson-Angus Scale (SAS)
- Columbia-Suicide Severity Rating Scale (C-SSRS)
- Vital signs (oral temperature, respiratory rate, pulse, systolic and diastolic blood pressure)
- Electrocardiogram parameters (heart rate, RR, PR, QRS, and QT)
- Clinical laboratory parameters (chemistry, hematology, and urinalysis; see [Table 2](#))
- Weight/BMI and Waist Circumference

See [Section 8.3.9.3](#) for more details on the AIMS, BARS, SAS and C-SSRS.

#### 13.1. Definition of Adverse Event

An AE is any untoward medical occurrence in a patient or clinical investigation subject administered a pharmaceutical product. The occurrence, which may or may not have a causal relationship with the investigational treatment, may include any clinical or laboratory change that does not commonly occur in that subject and is considered clinically significant.

Illnesses present prior to the subject signing the informed consent form (ICF) are considered to be pre-existing conditions and are documented on the medical history eCRF. Pre-existing conditions that worsen during the study are entered on the AE eCRF.

All out-of-range laboratory values will be deemed as clinically significant or not clinically significant by the investigator. Clinically significant values will be considered AEs and recorded as such on the eCRFs.

Pregnancy is not considered an AE, although a subject will be withdrawn from the study if a pregnancy occurs. As described in [Section 8.4.1](#), the pregnancy must be reported to Alkermes and additional follow-up may be required.

#### 13.2. Definition of Serious Adverse Event

An SAE is any AE, occurring at any dose and regardless of causality that meets one or more of the following criteria:

- Results in death
- Is life-threatening. The subject is at immediate risk of death from the reaction as it occurs. This does not include reaction that, had it occurred in a more severe form, might have caused death

- Requires inpatient hospitalization or prolongation of existing hospitalization. Hospital admission for elective surgery scheduled prior to study entry is not considered an SAE
- Results in disability/incapacity (eg, a substantial disruption of a person's ability to conduct normal life functions)
- Is a congenital anomaly/birth defect

Important medical events that may not result in death, be immediately life threatening, or require hospitalization may be considered to be SAEs when, based upon appropriate medical judgment, they may jeopardize the patient or subject and may require intervention to prevent one of the other outcomes listed above.

### **13.3. Relationship to Study Drug**

The assessment of study drug relationship to each AE will be reported on the appropriate source document (and SAE form, in the event of an SAE) by the investigator (or designated sub-investigator) according to his/her best clinical judgment. The criteria listed in [Table 3](#) should be used to guide this assessment. Please note that not all criteria must be present to be indicative of a particular drug relationship. All study drugs are considered "test drugs" for the purposes of the definitions listed in the table.

**Table 3: Adverse Event Causality Guidelines**

Relationship	Criteria for assessment
Definitely related	
There is evidence of exposure to the test drug.
 
AND
 
The temporal sequence of the AE onset relative to administration of the test drug is reasonable.
 
The AE is more likely explained by the test drug than by another cause.
 
Dechallenge (if performed) is positive.
 
Rechallenge (if feasible) is positive.
 
The AE shows a pattern consistent with previous knowledge of the test drug or test drug class.

Probably related	
There is evidence of exposure to the test drug.
 
AND
 
The temporal sequence of the AE onset relative to administration of the test drug is reasonable.
 
The AE is more likely explained by the test drug than by another cause.
 
Dechallenge (if performed) is positive.

Possibly related	
There is evidence of exposure to the test drug.
 
AND
 
The temporal sequence of the AE onset relative to administration of the test drug is reasonable.
 
The AE could have been due to another equally likely cause.
 
Dechallenge (if performed) is positive.

Probably not related	
There is evidence of exposure to the test drug.
 
AND
 
There is another more likely cause of the AE.
 
Dechallenge (if performed) is negative or ambiguous.
 
Rechallenge (if performed) is negative or ambiguous.

Definitely not related	
The subject did not receive the test drug.
 
OR
 
Temporal sequence of the AE onset relative to administration of the test drug is not reasonable.
 
OR
 
There is another obvious cause of the AE.

### 13.4. Monitoring and Recording of Adverse Events

AE data collection will begin after a subject signs the ICF and will continue until completion of the safety follow-up visit (Visit 7). Any AE or SAE having an onset after the safety follow-up visit will not be collected or reported unless the investigator feels that the event may be related to the study drug.

Subjects will be instructed by the investigator or designee to report the occurrence of any AE. All volunteered, elicited, and observed AEs are to be recorded on the AE eCRFs.

The investigator will assess all AEs regarding any causal relationship to the study drug (see [Section 13.3](#)), the intensity (severity) of the event, action taken, and subject outcome.

The following criteria should be used to guide the assessment of intensity (severity):

- **Mild:** Causes awareness of sign or symptom, but is easily tolerated; does not interfere with usual activities
- **Moderate:** Causes discomfort enough to interfere with usual activities
- **Severe:** Is incapacitating; results in inability to work or perform usual activities

All AEs will be followed until resolution, until deemed stable by the investigator, or until the subject is deemed by the investigator to be lost to follow-up.

For clinical study safety reporting purposes, the most recent version of the [Investigator's Brochure](#) will be used as the reference document to designate event expectedness.

Withdrawal from the study as a result of an AE and any therapeutic measures that are taken shall be at the discretion of the investigator. If a subject withdraws from the study for any reason, any ongoing AEs will be followed until resolution, until deemed stable by the investigator, or until the subject is deemed by the investigator to be lost to follow-up.

### 13.5. Reporting of Serious Adverse Events

All SAEs must be reported to PPD [REDACTED] within 1 business day of discovery, by emailing PPD [REDACTED] or faxing the report to the following:

Attention: PPD [REDACTED] Medical Monitor  
US Fax Number.: PPD [REDACTED]  
EU Fax Number: PPD [REDACTED]

The written report should be submitted on the SAE form provided for this purpose. The report must include the investigator's opinion as to whether the event is study drug-related. If this relationship is determined to be possibly, probably, or definitely related to study drug, evidence to support this assessment must also be provided.

## **14. STATISTICS**

### **14.1. Sample Size Considerations**

The planned sample size is 390 subjects in total, randomized 1:1:1 to ALKS 3831, olanzapine and placebo arms. This sample size will provide at least 90% power to show superiority for ALKS 3831 group when compared to placebo at the 2-sided alpha level of 0.05, assuming a 10-point improvement of PANSS total score at week 4, a standard deviation (SD) of 20, and a dropout rate of 30%.

### **14.2. General Statistical Methodology**

The statistical analysis methods are described below. Additional details will be provided in the Statistical Analysis Plan to be finalized before database lock and unblinding.

In general, summary statistics (n, mean, standard deviation [SD], median, minimum and maximum for continuous variables, and number [%] of subjects in each category for categorical variables) will be provided by treatment group for all variables.

Source data for the summary tables and statistical analyses will be presented as subject data listings.

All statistical tests and confidence intervals, unless stated otherwise, will be 2-sided and will be set at  $\alpha = 0.05$ .

#### **14.2.1. Study Populations**

##### **14.2.1.1. Safety Population**

The safety population includes all randomized subjects who receive at least 1 dose of study drug during the double-blind treatment period.

##### **14.2.1.2. Efficacy Population**

The full analysis set (FAS) population will be used for efficacy analysis and includes all subjects in the safety population who have at least one post-baseline PANSS assessment.

### **14.3. Demographics and Baseline Data**

Demographics and baseline characteristics such as gender, age, race, weight, BMI, and psychiatric history will be summarized by treatment group. If there are heterogeneities between study groups in any of the subject characteristics that are of clinical importance or could affect the treatment outcome, the impact of the imbalances will be investigated and, if necessary, appropriate adjustments made in the efficacy and safety analyses.

Medical history will be summarized for the safety population using the number of observations and percentage of subjects reporting each category.

## 14.4. Efficacy Analyses

Efficacy analyses will be based on the FAS population. Baseline for efficacy analysis is defined as the last non-missing efficacy assessment before the first dose of study drug in the double-blind treatment period. All statistical tests will be 2-sided hypothesis tests performed at the 5% significance level. All confidence intervals will be 2-sided 95% confidence intervals, unless specified otherwise.

### 14.4.1. Primary Endpoint

The primary efficacy endpoint is change from baseline in PANSS total score at Week 4.

For the primary efficacy endpoint, change from baseline in PANSS total score at week 4, analysis will be carried out using a mixed model with repeated measurements (MMRM) with an unstructured variance-covariance matrix based on the observed data. The model will include visit, treatment, and interaction term of visit and treatment as categorical variables, and baseline PANSS total score as a covariate. The statistical test will be carried out as follows:

The change from baseline in PANSS total score at Week 4 in ALKS 3831 group will be compared to that in the placebo group using superiority testing at two-sided alpha level of 0.05.

### 14.4.2. Key Secondary Endpoint

The key secondary endpoint is change from baseline in CGI-S score at Week 4.

The analysis will be carried out using MMRM as described for the primary endpoint.

### 14.4.3. Other Endpoints

- Change from baseline in PANSS total score and PANSS subscales (positive, negative, general psychopathology) by visit
- Change from baseline in MOAS score by visit
- Change from baseline in CGI-S by visit
- CGI-I at each postbaseline visit
- PANSS responders ( $\geq 30\%$  improvement from baseline in PANSS total score) by visit
- CGI-I responders (CGI-I score of 2 [much improved] or 1 [very much improved]) by visit
- Overall Response defined as: PANSS total score  $\geq 30\%$  improvement from baseline or CGI-I score of 1 or 2 by visit
- Change from baseline in PANSS-Excited Component (EC) score (comprised of 5 items, excitement, tension, hostility, uncooperativeness, and poor impulse control) by visit

For proportion of subjects exhibiting improvement on CGI-I assessment, a logistic regression based on last observation carried forward (LOCF) imputation for missing data will be used to

compare ALKS 3831 with placebo. The model will include treatment group, and baseline PANSS total score as covariates.

For all other endpoints, each point will be summarized by treatment groups for all visits. Each active group (ALKS 3831 or olanzapine) will be compared to placebo. For continuous outcome, a similar approach to that for PANSS total score will be used. For dichotomous outcome, a similar approach to that used for CGI-I improvement scores will be used. More details will be provided in the statistical analysis plan (SAP).

#### **14.5. Pharmacokinetic Analyses**

Listings will be provided for concentrations of olanzapine, samidorphan, and metabolites of interest. PK concentrations may be used in a subsequent population PK analysis conducted outside of this study.

#### **14.6. Safety Analyses**

The safety analysis will be carried out using the Safety Population. For each safety parameter, the last assessment of the parameter before the first dose of randomized study drug will be used as the baseline for all analyses of that safety parameter. Safety endpoint will include adverse events (AEs), clinical laboratory parameters, vital signs, electrocardiographic (ECG) parameters, Columbia–Suicide Severity Rating Scale (C-SSRS) scores, body weight, BMI, waist circumference, AIMS, BARS, and SAS. All safety analyses will be based on observed data only, and no missing values will be imputed.

Reported adverse event terms will be coded using the Medical Dictionary for Regulatory Activities (MedDRA) and summarized by preferred term and system organ class categories.

Safety assessments will be summarized using descriptive statistics along with supportive listings.

The number and percentage of TEAEs will be summarized by treatment group and overall by system organ class, and preferred terms within each system organ class. SAEs and AEs resulting in treatment discontinuation will also be summarized.

Observed values and change from baseline in laboratory parameters, weight, BMI, waist circumference, vital signs, and ECG parameters will be summarized by treatment group and study visit.

The number and percentage of subjects who have met potentially clinically significant (PCS) criteria at any post-baseline visit will be summarized by treatment group labs, vitals, weight, and ECG parameters. Supporting listings will be provided.

The number and percentage of subjects with shifts in laboratory and extra pyramidal symptom (EPS) parameters (AIMS, BARS, and SAS) will also be summarized by treatment group.

Prior and concomitant medication use will be summarized by World Health Organization (WHO) Drug Dictionary Anatomical Therapeutic Class (ATC) code and by treatment group.

The number and percentage of subjects with C-SSRS assessments of suicidal ideation and behavior will also be summarized.

Listings will be provided for all safety endpoints.

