### 7.2.1. Psychiatric Exclusion Criteria

1. Subject has had a psychiatric hospitalization for more than 30 days during the 90 days before screening
2. Subject initiated first antipsychotic treatment within the past 12 months, or <1 year has elapsed since the initial onset of active-phase of schizophrenia symptoms.
3. Subject has any of the following psychiatric conditions per DSM-5 criteria, as assessed by the MINI. Conditions not assessable by the MINI should be assessed by clinical judgment
  - Diagnosis of schizoaffective disorder or bipolar I or II disorder, or current, untreated or unstable major depressive disorder (according to DSM-5 Criteria)
  - Clinically significant cognitive difficulties including dementia, delirium, or amnesic syndromes, or any other cognitive disorder present within the past 2 years that could interfere with participation in the study
  - Drug-induced or toxic psychosis
  - Any other psychiatric condition that could interfere with participation in the study
4. Subject poses a current suicide risk in the opinion of the investigator or as confirmed by the following:
  - Answers “Yes” on items 4 or 5 (C-SSRS-ideation) with the most recent episode occurring within the past 2 months, or answers “Yes” to any of the 5 items (C-SSRS-behavior) with an episode occurring within the last year
5. Subject’s PANSS score improves  $\geq 30\%$  from Visit 1 to Visit 2

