-  The “Baseline/Screening” version of the C-SSRS will be used at screening; the “Since Last Visit” version to be used at all other scheduled visits.
-  Abnormal movement scales include the following: Abnormal Involuntary Movement Scale (AIMS), Barnes Akathisia Rating Scale (BARS), and Simpson-Angus Scale (SAS).
-  With the exception of the screening visit, the PANSS should be administered before other psychiatric assessments at each specified study visit.
-  The MOAS will be performed on all subjects at Visits 2, 3 and 4 and only on inpatient subjects at Visits 5 and 6.
-  Only for inpatient subjects
-  CGI-S will be administered at the Screening Visit using the structured interview guide for global impressions (SIGGI)
-  The informed consent form for the open-label extension, ALK3831-A306, must be distributed to subjects by the end of treatment. However, the form may be distributed to subjects earlier at the investigator's discretion.
-  Emergency treatment card to be dispensed at randomization (Visit 2), confirmed at subsequent time points, and collected at Visit 6, EOT.
-  Subjects will be admitted to the inpatient unit on the same day as their screening assessments if they are not already inpatient.
-  Subjects may be discharged at Day 15, Day 22, or Day 29 if they meet discharge criteria. Subjects not meeting discharge criteria at Day 29 may remain inpatient for up to 1 additional week and may be discharged from the inpatient unit at any point during this week at the investigator's discretion.
-  During the inpatient stay, study drug will be administered daily by study staff, preferably at bedtime. Upon discharge, subjects will be given study drug to take daily, preferably at bedtime though dose timing may be adjusted at the investigator's discretion based on tolerability.

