3.9. Safety Analysis

3.9.1. Adverse Events

Adverse events will be coded by System Organ Class and Preferred Term using the Medical Dictionary for Regulatory Activities (MedDRA[®]) Version 19.0 or higher. The verbatim term will be included in the AE listings.

An AE (classified by preferred term) will be considered as treatment-emergent AE (TEAE) if the event is newly occurring or worsening on or after the date of first dose of study drug.

The number and percentage of subjects reporting TEAEs in each treatment group during the double-blind period will be presented by treatment group for the following categories:

- System organ class and preferred term
- Preferred terms in decreasing frequency, and also including the following subsets:
 - Experienced by $\geq 2\%$ of subjects in any treatment group
 - Experienced by $\geq 5\%$ of subjects in any treatment group and ≥ 2 times of placebo group
- System organ class, preferred term, and severity
- System organ class, preferred term for severe TEAEs
- System organ class, preferred term, and relationship
- System organ class, preferred term for drug-related TEAEs

If more than one AE is coded to the same preferred term for the same subject, the subject will be counted only once for that preferred term using the most severe and most related occurrence for the summarization by severity and by relationship to study drug.

In addition, the number and percentage of subjects reporting AEs during the Safety Follow-up Period will be tabulated by the system organ class, preferred term and treatment group.

The number and percentage of subjects who have serious adverse events (SAE) and AEs leading to premature discontinuation from the treatment will be summarized by preferred term and treatment group and will be sorted by decreasing frequency for ALKS 3831 group.

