3.9.2. Clinical Laboratory Parameters

Laboratory parameters will be presented in conventional (ie, US) units. Only scheduled laboratory parameters will be included in the summaries. All laboratory data, including those collected at unscheduled visits, will be included in the listings.

Laboratory results (baseline and change from baseline) for the Safety population for chemistry and hematology parameters will be summarized by treatment group and by visit.

Number (percentage) of subjects with potentially clinically significant (PCS) values at any post-baseline visit, will be summarized by treatment group. PCS criteria are presented in [Table 1](#). The denominator is all subjects with non-PCS baseline and at least one post-baseline assessment in the Safety Population and the numerator is the number of subjects with non-PCS baseline and PCS at post-baseline. All PCS values including baseline PCS values will be included in supportive listings.

Shift tables for selected metabolic parameters (glucose, total cholesterol, LDL, HDL, tryglyceride, and HbA1c) and liver function tests will be presented. The criteria are summarized in [Table 2](#), [Table 3](#) and [Table 4](#).

Table 1: Criteria of Potentially Clinically Significant (PCS) Abnormality for Selected Analytes

Parameters	Criteria
Chemistry	
Albumin	<2.5 g/dL
Alkaline Phosphatase (U/L)	$\geq 3 \times \text{ULN}$
Alanine Aminotransferase (U/L)	$\geq 3 \times \text{ULN}$
Aspartate Aminotransferase (U/L)	$\geq 3 \times \text{ULN}$
Bilirubin, Total	$\geq 2.0 \text{ mg/dL}$
Blood Urea Nitrogen	>30 mg/dL
Cholesterol, Random	>300 mg/dL
Cholesterol, Fasting	$\geq 240 \text{ mg/dL}$
Cholesterol, HDL Fasting	$\leq 30 \text{ mg/dL}$
Cholesterol, LDL Fasting	$\geq 160 \text{ mg/dL}$
Creatine Kinase (U/L)	$\geq 3 \times \text{ULN}$
Creatinine	$\geq 2.0 \text{ mg/dL}$
Glucose, Random	<50 mg/dL or $\geq 200 \text{ mg/dL}$
Glucose, Fasting	<50 mg/dL or $\geq 126 \text{ mg/dL}$
Potassium	<3 mmol/L or >5.5 mmol/L
Lactate Dehydrogenase (U/L)	$> 3 \times \text{ULN}$
Prolactin (Female)	>30 ng/mL
Prolactin (Male)	>20 ng/mL
Sodium	<130 mmol/L or >150 mmol/L
Triglycerides, Fasting (Female)	$\geq 120 \text{ mg/dL}$
Triglycerides, Fasting (Male)	$\geq 160 \text{ mg/dL}$

Table 1: Criteria of Potentially Clinically Significant (PCS) Abnormality for Selected Analytes (Continued)

Parameters	Criteria
Hematology	
Eosinophils	$>1.0 \times 10^3/\mu\text{L}$
Hematocrit (Female)	$\leq 32\%$
Hematocrit (Male)	$\leq 37\%$

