3.9.5. Columbia-Suicide Severity Rating Scale (C-SSRS)

The C-SSRS is a questionnaire used to measure the presence and intensity of suicidal ideation and behavior.

Suicidal behavior and suicidal ideation will be summarized descriptively. The number of subjects with suicidal ideation and suicidal behavior during the double-blind treatment period will be summarized by treatment group when applicable.

Supportive tabular display of subjects with all values will be provided, including subject ID number, treatment group, visit number, intensity of suicidal ideation, suicidal behavior type, and lethality of suicidal behavior.

Table 8: C-SSRS Categories for Analysis

Category	C-SSRS Item response is “YES”
Suicidal behavior	Preparatory acts or behavior Aborted attempt Interrupted attempt Actual attempt Complete suicide
Suicidal ideation	Wish to be dead Non-specific active suicidal thoughts Active suicidal ideation with any methods (not plan) without intent to act Active suicidal ideation with some intent to act, without specific plan Active suicidal ideation with specific plan and intent

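### The planned C-SSRS counts do not use pre-dose status, so ideation persisting from entry (mainly items 1-3) is mixed with new ideation in the by-arm comparison

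*Protocol*

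**What the plan says.** - **The count.** Protocol 14.6: "The number and percentage of subjects with C-SSRS assessments of suicidal ideation and behavior will also be summarized". SAP 3.9.5: "The number of subjects with suicidal ideation and suicidal behavior during the double-blind treatment period will be summarized by treatment group when applicable". SAP Table 8 places a subject in the ideation category on a Yes to any of the five ideation items, and in the behavior category on a Yes to any of five kinds of behavior. Neither text gives a new-or-worsened rule, a split by pre-dose status, a C-SSRS shift table or a denominator.
- **The baseline.** Protocol 14.6 names C-SSRS scores among the safety endpoints and says of each parameter that "the last assessment of the parameter before the first dose of randomized study drug will be used as the baseline for all analyses". Protocol Table 1 schedules the C-SSRS at screening and predose on Day 1. Footnote 11 makes the Since Last Visit form the "version to be used at all other scheduled visits", so the baseline is the Day 1 form.
- **Entry.** Exclusion 4 (Protocol 7.2.1) bars a Yes on "items 4 or 5 (C-SSRS-ideation) with the most recent episode occurring within the past 2 months", a Yes on any behavior item with an episode in the last year, and anyone the investigator considers a current risk. It does not name ideation items 1-3.
- **Other safety counts.** An adverse event is treatment-emergent "if the event is newly occurring or worsening on or after the date of first dose of study drug" (SAP 3.9.1). For laboratory values, "The denominator is all subjects with non-PCS baseline and at least one post-baseline assessment in the Safety Population" (SAP 3.9.2). Vital-sign and ECG counts (SAP 3.9.3.1 and 3.9.3.3) likewise require a non-PCS or normal baseline.

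**The concern.** Two quantities enter one number. The first is persistence: a subject with ideation at entry says Yes again after dosing, perhaps while improving. The second is onset: a subject without ideation at entry reports it on treatment. Onset is the drug-safety question. Persistence also reflects how well treatment works, and these are acutely ill subjects in a trial of an effective drug class.

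Safety and tolerability are the secondary objective. If persistence supplies most of the events, the by-arm table says little about onset, and a reader cannot separate the two from it. The subject-level display in SAP 3.9.5 would let someone construct an emergent count afterwards, but under a rule chosen once the data are known.

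**Working it through.** **The plan's own figures.** The documents give no C-SSRS rate and no power for it, so there is no C-SSRS figure to reproduce. The 130 per arm (SAP 2) comes from the PANSS comparison. That figure does reproduce: 130 × 0.7 = 91 evaluable per arm, a 10-point difference and an SD of 20 give power 0.92, against at least 90% stated. It does not bear on suicidality.

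**Formula.** Let b be the share with pre-dose ideation, p the share of those who report it again after dosing, and e the new-onset share among the rest. The planned count estimates

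R = b·p + (1 − b)·e.

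The ratio of the two arms' counts is a weighted average:

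R_drug / R_placebo = w·(p_drug / p_placebo) + (1 − w)·(e_drug / e_placebo), with w = b·p_placebo / R_placebo.

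The onset ratio is thus pulled towards the persistence ratio. If persistence is no higher on drug, an onset ratio above 1 is always diluted.

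**Inputs, all assumed except N.** N = 130 per arm (SAP 2); e = 2% placebo and 4% ALKS 3831, a true ratio of 2.0; b = 5%, 10%, 20%; p = 60% on placebo, and 60% or 30% on ALKS 3831.

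| b | Placebo R | Drug R, p = 60% | Ratio | Drug R, p = 30% | Ratio |
|---|---|---|---|---|---|
| 5% | 0.030 + 0.019 = 4.9% | 0.030 + 0.038 = 6.8% | 1.39 | 0.015 + 0.038 = 5.3% | 1.08 |
| 10% | 0.060 + 0.018 = 7.8% | 0.060 + 0.036 = 9.6% | 1.23 | 0.030 + 0.036 = 6.6% | 0.85 |
| 20% | 0.120 + 0.016 = 13.6% | 0.120 + 0.032 = 15.2% | 1.12 | 0.060 + 0.032 = 9.2% | 0.68 |

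Check at b = 10%: w = 0.060 / 0.078 = 0.77, and 0.77 × 1 + 0.23 × 2 = 1.23.

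**Difference scale.** With equal persistence the difference is (1 − b)(e_drug − e_placebo): 1.9, 1.8 and 1.6 percentage points in place of 2.0. On this scale the loss is small; it is the ratio that suffers.

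**When the sign turns.** The two counts are equal at b = (e_drug − e_placebo) / [(e_drug − e_placebo) + (p_placebo − p_drug)]. For 60% against 30% persistence this is 0.02 / (0.02 + 0.30) = 6%. For 50% against 40% it is 0.02 / (0.02 + 0.10) = 17%. With equal persistence the sign never turns.

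**What an emergent count could show.** At b = 10%, 117 subjects per arm start without ideation, and 2.3 against 4.7 new cases are expected. The standard error of the log ratio is √(1/2.34 + 1/4.68 − 2/117) = 0.79, so an approximate 95% interval around 2.0 runs from 0.43 to 9.4. The chance that drug shows no more cases than placebo is about 24%, and the chance of Fisher p < 0.05 about 6%.

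**The case against.** **The any-Yes count is a fair comparison.** Randomization balances entry ideation in expectation, so the table validly compares on-treatment suicidality. That stands. It answers a different question from emergence, which is why it should stay.

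**Suicide-related adverse events are summarized by arm.** SAP 3.9.1.1 does this by preferred term and SMQ, and SAP 3.9.1 applies a new-or-worsening rule to TEAEs. This is real mitigation, but it rests on adverse event reporting and does not use the structured scale.

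**The serious categories are close to emergent already.** Exclusion 4 screens out recent items 4-5 and behavior, and Protocol Table 1 repeats the eligibility review predose at Visit 2. That also stands; the problem lies in ideation items 1-3.

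**Power.** The analysis is descriptive, and on the assumed rates neither table could reliably detect a doubling. True, but with so few events a handful of persistent cases can dominate the table.

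**Stronger readings that a reader might infer.**
- *The count will hide or reverse a true signal.* Reversal needs persistence to be lower on drug and pre-dose ideation above a threshold. The documents quantify neither.
- *The predose Day 1 form is counted as on-treatment.* Table 1 does place Visit 2 under the double-blind heading, but the entry is footnoted as predose and Protocol 14.6 makes it baseline.
- *The Day 43 C-SSRS is summarized nowhere.* The Protocol 14.6 count and the first summary sentence of SAP 3.9.5 carry no period limit, all values are displayed by visit, and the mock tables are a separate document.

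**Conclusion.** The point holds for ideation. Both documents plan a count that ignores a baseline the protocol itself defines, while the SAP conditions treatment-emergent adverse events and laboratory, vital-sign and ECG counts on pre-dose status. That standard is not universal: the abnormal-movement counts in SAP 3.9.4 state no baseline condition either, though they are labelled treatment emergent.

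Dilution of the ratio needs only that some entry ideation persists and that persistence is not higher on drug. Reversal is possible, not shown. On the assumed rates a true ratio of 2.0 reads 1.39, 1.23 and 1.12 with equal persistence, and 1.08, 0.85 and 0.68 with 60% against 30%. These figures show the mechanism; they do not predict the trial's result. Behavior and items 4-5 are barely touched. The change is worth making before unblinding because it is cheap and fixes the rule in advance. It does not invalidate the planned table.

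**What to change.** In SAP 3.9.5, with matching words in Protocol 14.6, keep the any-Yes count and add by arm:

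1. The number and percentage with new or worsened ideation after first dose (Visits 3-6) relative to the pre-dose C-SSRS. The denominator is Safety Population subjects with a pre-dose and at least one post-dose C-SSRS.
2. A shift table from pre-dose to worst post-dose ideation category (0-5), which also shows pre-dose prevalence.

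Use the Day 1 predose form as baseline, as Protocol 14.6 implies. Give a second version against the worse of Day 1 and the recent-period column of the screening form, once the recall window of that column is stated; the form in Protocol Appendix H leaves the number of months open. The two months of exclusion 4 would be a natural choice.

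State that the on-treatment count starts after first dose. Show Visit 7 as a separate row, noting that Visit 7 is not required for subjects who enter the extension study and that other antipsychotics are allowed in follow-up.

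The cost is SAP wording and one more table from data already collected; sample size and procedures do not change. A count against the worst pre-dose category can miss recurrence at the same level and so under-count, which is a further reason to keep the existing count beside it.
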